### **9.7.1 Primary Objective**

Descriptive statistics (frequency, count, and percentage) will be provided to assess safety outcomes (Grade 3 and 4 events) and their management and outcomes. Time to onset and time to resolution will be summarized with mean, median, minimum, maximum, and standard deviation (SD).

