## 4.9 Study Analysis

The data provided for pediatric patients will be divided into 2 cohorts, based on age at time of first dose of nivolumab monotherapy, ipilimumab monotherapy, or nivolumab in combination with ipilimumab treatment (index date). Cohort 1 will include patients 12 to under 18 years old at time of enrollment, and Cohort 2 will include patients < 12 years of age at the time of enrollment. Patients treated before the nivolumab or ipilimumab marketing approval date will be included and assigned to the appropriate age-based cohort, regardless of timing with respect to date of approval. Interim data on pediatric patients treated with nivolumab monotherapy, ipilimumab monotherapy, or nivolumab in combination with ipilimumab will be reported by Bristol-Myers Squibb Company to the Pharmacovigilance Risk Assessment Committee in the Periodic Safety Update Report, in the interim study report, and in the final study report.

Descriptive statistics will be used to assess baseline patient characteristics, disease and other clinical characteristics, and treatment patterns. Descriptive statistics will also be used to assess safety outcomes (Grade 3 and 4 events) and observations related to parameters for growth and sexual maturation. Additionally, premature or delayed puberty will be analyzed based on gender and normal sexual maturation scales.

A description of patient and tumor characteristics for all pediatric patients receiving alternative therapies will be provided for the overall treatment landscape for this patient population.

Kaplan-Meier methodology will be used for the assessment of OS and progression-free survival.

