#### **9.1.1 Primary Endpoint**

The primary endpoints will be the frequency of Grade 3 and 4 treatment-related AEs and their management and outcomes.

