## **9.3 Variables**

### **9.3.1 Outcomes/Endpoint Variables**

Grade 3 and 4 treatment-related AEs will be collected according to the current Common Terminology Criteria for Adverse Events (CTCAE) version at the time of AE collection.

The DMTR provides detailed information on patient and tumor characteristics, diagnostics, treatment strategies, AEs, time to progression, and survival.

Variables include the following:

- Grade 3 and 4 treatment-related AEs, including:
  - blood disorders, such as leukopenia, thrombocytopenia, anemia
  - neuropathy
  - gastrointestinal, such as colitis, perforation
  - skin toxicity
  - uveitis

- endocrinopathy, such as adrenal insufficiency, pituitary insufficiency, thyroid insufficiency, diabetes mellitus
- hepatitis
- hypersensitivity
- nephritis and renal dysfunction
- pneumonitis
- myocarditis
- other
- Grade 3 to 4 treatment-related AEs onset date
- Grade 3 to 4 treatment-related AEs resolution date
- Grade 3 to 4 treatment-related AEs action taken with nivolumab monotherapy, ipilimumab monotherapy, or nivolumab in combination with ipilimumab treatment: dose interruption, discontinuation
- Grade 3 to 4 treatment-related AEs management: concomitant (interventional) medication or procedure
- Grade 3 to 4 treatment-related AEs outcome: resolved, resolved with sequelae, unresolved, death, unknown
- Parameters related to growth and sexual maturation (eg, height, weight, Tanner stage)
- Efficacy outcomes: time to progression, PFS, OS

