### **9.7.2 Secondary Objectives**

Descriptive statistics will be used to assess:

- Baseline characteristics, disease, and other clinical characteristics
- Treatment patterns, such as exposure to nivolumab monotherapy, ipilimumab monotherapy, or nivolumab in combination with ipilimumab (dose, frequency, treatment duration or number of infusions administered), and changes in nivolumab monotherapy, ipilimumab monotherapy, or nivolumab in combination with ipilimumab treatment following a Grade 3 to 4 AE, including

reasons for discontinuation of nivolumab or ipilimumab (including toxicity) and treatment with any subsequent therapies

- Observations related to parameters for growth and sexual maturation (height, weight, and Tanner stage)

Additionally, premature or delayed puberty will be analyzed based on gender and normal sexual maturation scales.

General descriptive statistics will include mean, median, minimum, maximum, and SD for continuous variables; count and percentages will be used to examine categorical variables.

Long-term outcomes for survival, time to progression, and PFS will be defined and analyzed as follows:

OS is defined as the time between the date of first treatment with study drug and the date of death. For subjects without documentation of death, OS will be censored on the last date the subject was known to be alive. OS medians and rates at several points of time (eg, at year 1 year, year 5), will be estimated using the Kaplan-Meier methodology for each treatment group.

Time to progression is defined as time from the first treatment with study drug to the date of the first documented progression, as assessed by investigator per the Response Evaluation Criteria in Solid Tumors (RECIST) v1.1.

The PFS is defined as the time between the date of the first treatment with study drug and the date of first documented tumor progression, based on investigator assessments (per RECIST v1.1), or death due to any cause, whichever occurs first. Subjects who die without a reported progression will be considered to have progressed on the date of their death. Subjects who did not progress or die will be censored on the date of their last (most recent) date of visit to the treating physician in the hospital.

Median PFS in each treatment group will be derived from the Kaplan Meier estimate.

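### Time to resolution of Grade 3-4 AEs is summarised by mean, median and SD, which only events with a resolution date can enter, so the figure understates how long toxicity lasts across all events

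*Protocol*

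**What the plan says.** Section 9.7.1 (Primary Objective) plans counts and percentages for Grade 3-4 events, their management and their outcomes. It then fixes the statistics for the two timing variables: "Time to onset and time to resolution will be summarized with mean, median, minimum, maximum, and standard deviation (SD"). It gives no rule for an event without a resolution date.

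Section 9.3.1 collects "Grade 3 to 4 treatment-related AEs resolution date" and defines the outcome variable as "Grade 3 to 4 treatment-related AEs outcome: resolved, resolved with sequelae, unresolved, death, unknown". The event types listed there include "endocrinopathy, such as adrenal insufficiency, pituitary insufficiency, thyroid insufficiency, diabetes mellitus".

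Section 9.1.1 reads: "The primary endpoints will be the frequency of Grade 3 and 4 treatment-related AEs and their management and outcomes". Section 9.5 says that follow-up differs between patients according to index date.

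The protocol does recognise censoring elsewhere. Section 9.7.2 gives censoring rules for OS and PFS, and section 4.9 says "Kaplan-Meier methodology will be used for the assessment of OS and progression-free survival".

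**The concern.** Time to resolution is a censored variable. An event still ongoing at last contact has a duration known only to exceed the time observed so far, and an event that ends in death never resolves. A mean, an SD or a simple median cannot use either kind. They are computed on the events that did resolve, and short events resolve before last contact more often than long ones.

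The section concerned serves the primary objective, and that objective singles out endocrine events. A reader of the interim or final report will take a mean or median time to resolution as an answer to how long Grade 3-4 toxicity lasts. As specified, it answers a narrower question: how long toxicity lasted in those events that resolved. Nothing in section 9.7.1 says so.

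**Working it through.** The plan states no figure to reproduce: it gives no AE duration, no expected number of events and no expected share unresolved. The check has two parts.

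**1. Which events can enter (sections 9.3.1 and 9.7.1).**

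| AE outcome | Resolution date | Enters mean, median, SD |
|---|---|---|
| resolved | yes | yes |
| resolved with sequelae | yes | yes |
| unresolved | none | no |
| death | none | no |
| unknown | none or uncertain | no, unless a date happens to exist |

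Entering the last-contact date as if it were the resolution date would not help, because it too cuts the ongoing events short.

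**2. Illustrative size.** All inputs here are assumptions, not figures from the protocol. Let a share p of events never resolve, and let the others resolve exponentially with median m. The probability that an event is still unresolved at time t is

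S(t) = p + (1 − p) · 2^(−t/m).

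Setting S(t) = 0.5 gives the median over all events:

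t = m · log2[(1 − p)/(0.5 − p)] for p < 0.5, and not reached for p ≥ 0.5.

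With m = 2 months and p = 0.30: (0.70/0.20) = 3.5; log2(3.5) = 1.807; t = 2 × 1.807 = 3.6 months. The median among resolving events is 2 months by assumption, so a resolved-only median is at most about 2.

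A simulation with m = 3 months (200,000 events per scenario, follow-up after onset uniform, no deaths) gave:

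| Share never resolving | Resolved-only median, follow-up 1-12 months | Resolved-only median, follow-up 1-60 months | All-event Kaplan-Meier median, follow-up 1-60 months | Formula |
|---|---|---|---|---|
| 0% | 1.95 | 2.79 | 3.0 | 3 × log2(2) = 3.0 |
| 10% | 1.96 | 2.79 | 3.5 | 3 × log2(2.25) = 3.5 |
| 25% | 1.95 | 2.79 | 4.8 | 3 × log2(3) = 4.8 |
| 40% | 1.96 | 2.79 | 7.7 | 3 × log2(6) = 7.8 |
| 50% | 1.93 | 2.79 | not reached | not reached |

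The gap has two sources. One is truncation: with short follow-up, the slower resolvers are lost as well (1.95 against 3.0 months even when every event eventually resolves). The other is a change of question, from resolving events to all events. With long follow-up the second dominates. For m = 2 and p = 0.30, a mean follow-up of 60 months gives a resolved-only median of 1.96, so 2.00 − 1.96 = 0.04 months is truncation and 3.61 − 2.00 = 1.61 months is the change of question.

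A small constructed case shows the same thing without a model. Suppose five events resolve at 1, 2, 3, 4 and 6 months and three are ongoing at 24, 36 and 60 months. The resolved-only mean is 16/5 = 3.2 and the median 3. The Kaplan-Meier median is 4, and 3 of 8 events have lasted two years or more, which the summary does not show.

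**The case against.** The strongest reply is that nothing is hidden. The sentence before the one quoted from section 9.7.1 already plans counts and percentages of outcomes, so the numbers unresolved, fatal and unknown will be reported. That stands, and it limits the harm. It does not repair the duration figure, which appears separately and without a label.

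Second, time to resolution is not itself an endpoint. Section 9.1.1 names frequency, management and outcomes, and outcome is a categorical variable. Growth and puberty are assessed through their own measurements. This stands: the statistic is a supporting descriptive one.

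Third, much of the illustrated gap is a change of estimand, and the insensitivity of the resolved-only median to the never-resolving share follows from how the simulation was built. This also stands. But the plan does not say that it wants the narrower quantity, and a reader would not assume it.

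Fourth, fewer than 10 exposed patients a year (section 9.5), spread over six sub-cohorts and twelve AE categories, cannot support estimates by category. That is right, and it shapes the fix.

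Two stronger readings are tempting but not supported:

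- A reader might infer that the Q4 2026 interim report is affected most because follow-up is short. Ipilimumab data collection began in Q2 2019, and the notes to Table 6-1 include patients of all three treatments whose therapy started before data collection, so short follow-up at the interim cannot be presumed.
- A reader might infer that time to progression suffers in the same way. Section 9.7.2 says only "Time to progression is defined as time from the first treatment with study drug to the date of the first documented progression", as assessed by the investigator, without a censoring rule. But it places this variable with OS and PFS, apart from the general mean and SD sentence. The missing detail is of a kind that an SAP commonly supplies, and PFS already covers progression with censoring.

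**Conclusion.** The point holds in limited form. For time to resolution, section 9.7.1 names statistics that can use only events with a resolution date, although section 9.3.1 provides for events that have none. This is a stated rule, not something left open. Because ongoing events drop out, the result understates how long Grade 3-4 toxicity lasts across all events. The direction rests on the ongoing events. Fatal events have no time to resolution at all and need separate handling, and for unknown outcomes the direction is undetermined. Time to onset, which is defined only where an event occurred, is not affected in this way.

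The size cannot be derived from the documents. The 2 against 3.6 months illustrates one assumed case; under the other assumptions shown, the all-event median ranges from close to the resolved-only figure to not reached. The study is descriptive, no decision rule depends on this statistic, and outcome counts are planned. It is worth correcting, but it does not threaten the study.

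**What to change.** In section 9.7.1, replace the summary of time to resolution with an estimate over all Grade 3-4 treatment-related events, and over endocrine events where numbers allow:

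- Use the cumulative incidence of resolution, with events ongoing at last contact censored there and death as a competing event. Where no event ends in death, this equals one minus Kaplan-Meier.
- Report the median with 'not reached' where that applies.
- Keep mean, median, minimum, maximum and SD only if labelled 'resolved events only', with the numbers unresolved, fatal and unknown, and their follow-up, shown beside them.
- Do not attempt estimates for every AE category. Where events are few, a listing of each event with its duration and status tells the reader more.

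The resolution date and the outcome are already collected under section 9.3.1, as is the onset date. The cost is a change of wording and slightly more programming. Because section 9.6 leaves data management with the registry, which supplies aggregate information, the request has to be agreed with it. The estimates will be imprecise at this sample size, and the report should say so.

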### **9.7.2 Secondary Objectives**

Descriptive statistics will be used to assess:

- Baseline characteristics, disease, and other clinical characteristics
- Treatment patterns, such as exposure to nivolumab monotherapy, ipilimumab monotherapy, or nivolumab in combination with ipilimumab (dose, frequency, treatment duration or number of infusions administered), and changes in nivolumab monotherapy, ipilimumab monotherapy, or nivolumab in combination with ipilimumab treatment following a Grade 3 to 4 AE, including

reasons for discontinuation of nivolumab or ipilimumab (including toxicity) and treatment with any subsequent therapies

- Observations related to parameters for growth and sexual maturation (height, weight, and Tanner stage)

Additionally, premature or delayed puberty will be analyzed based on gender and normal sexual maturation scales.

General descriptive statistics will include mean, median, minimum, maximum, and SD for continuous variables; count and percentages will be used to examine categorical variables.

Long-term outcomes for survival, time to progression, and PFS will be defined and analyzed as follows:

OS is defined as the time between the date of first treatment with study drug and the date of death. For subjects without documentation of death, OS will be censored on the last date the subject was known to be alive. OS medians and rates at several points of time (eg, at year 1 year, year 5), will be estimated using the Kaplan-Meier methodology for each treatment group.

Time to progression is defined as time from the first treatment with study drug to the date of the first documented progression, as assessed by investigator per the Response Evaluation Criteria in Solid Tumors (RECIST) v1.1.

The PFS is defined as the time between the date of the first treatment with study drug and the date of first documented tumor progression, based on investigator assessments (per RECIST v1.1), or death due to any cause, whichever occurs first. Subjects who die without a reported progression will be considered to have progressed on the date of their death. Subjects who did not progress or die will be censored on the date of their last (most recent) date of visit to the treating physician in the hospital.

Median PFS in each treatment group will be derived from the Kaplan Meier estimate.

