### **9.2 Setting**

In the Netherlands, all pediatric patients are treated at 1 hospital, PMC. Therefore, the data for this study will be collected from this institution. Data collection is planned for approximately 10 years to obtain long-term follow-up on all enrolled pediatric melanoma patients treated with nivolumab monotherapy, ipilimumab monotherapy, or nivolumab in combination with ipilimumab.

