## 9.4 Data Sources

Data will be abstracted annually and retrospectively from medical charts (secondary use of data) from all pediatric melanoma patients enrolled in the DMTR. Trained data managers will coordinate and perform data collection in the melanoma centers. The Dutch Institute for Clinical Auditing will supervise data collection and management; oncologists will supervise the registration process and confirm all results at the patient level.

Data are entered into the DMTR electronic case report form (eCRF) for all patients receiving treatment at PMC. The evaluation of nivolumab- and ipilimumab-treated pediatric melanoma patients for this PASS will be carried out using data from the DMTR. Given the comprehensive

list of information that is already collected in the current DMTR eCRF, the likelihood that important data will be missed is small.

Additional data concerning outcomes related to growth and sexual maturation (eg, height, weight, Tanner stage) among nivolumab- or ipilimumab-treated pediatric patients that are not specified in the current DMTR data specifications will be abstracted via a pediatric-specific case report form (CRF) annex to the current eCRF. The special pediatric-specific CRF annex ([Annex 4](#)), was designed in collaboration with the participating pediatric oncologists and the DMTR scientific board.

The DMTR collects and analyzes Grade 3 and 4 treatment-related AEs (according to the current CTCAE version at the time of AE collection), data associated with the treatment of melanoma and clinical outcomes of all Dutch patients diagnosed with advanced (unresectable or metastatic) melanoma, or melanoma with involvement of lymph nodes or metastatic disease who have undergone complete resection. Grade 1 and 2 events are not captured by the DMTR. Death is recorded as a consequence of a Grade 3 or 4 toxicity, or as a reason for treatment discontinuation, rather than reporting as a Grade 5 event. Furthermore, the DMTR CRF includes queries for AE terms specific to the immune-mediated nature of the toxicity associated with immune-modulating therapies such as nivolumab and ipilimumab.

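### PFS is censored at the last physician visit whether or not disease status was assessed there, so it can be overstated where visits outlast tumour assessment

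*Protocol*

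**What the plan says.** Section 9.7.2 of the protocol defines a PFS event as "first documented tumor progression, based on investigator assessments (per RECIST v1.1), or death due to any cause, whichever occurs first". A death with no earlier progression on record is an event on the day of death: "Subjects who die without a reported progression will be considered to have progressed on the date of their death". All other patients are "censored on the date of their last (most recent) date of visit to the treating physician in the hospital".

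The summary named for PFS is the median: "Median PFS in each treatment group will be derived from the Kaplan Meier estimate". For OS the same section names medians and also rates at time points such as years 1 and 5.

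The setting is routine care. Section 9.4 says "Data will be abstracted annually and retrospectively from medical charts", and section 9.2 says "Data collection is planned for approximately 10 years to obtain long-term follow-up". No section gives a tumour-assessment schedule, a rule for missed assessments, or a link between the censoring visit and a disease assessment.

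**The concern.** The event and the censoring date come from two different observation processes. Progression enters the analysis only through an investigator assessment per RECIST v1.1. Progression-free time is extended by any later visit to the treating physician, whether or not disease status was recorded. On a strict reading, progression that the physician notes without a RECIST assessment is not an event, while the visit at which it was noted still adds progression-free time.

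Follow-up is long and has aims beyond tumour control, notably growth and sexual maturation, so visits may go on after tumour assessment has ended. A progression missed in that interval keeps the patient in the risk set as progression-free until death or the last visit, and the PFS curve is then too high.

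A second, smaller matter is that the median is the only PFS summary named. With few patients per treatment group it may not be reached, and the report would then carry no PFS estimate.

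Section 9.7.2 fixes the censoring rule itself, so that rule is not a detail left to the SAP.

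**Working it through.** The protocol states no PFS figure, so there is nothing to reproduce. Every input below is an assumption, apart from the event and censoring rules of section 9.7.2.

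**1. Direction.** The Kaplan-Meier estimate is S(t) = ∏(1 − dᵢ/nᵢ). With the same events, later censoring can only enlarge the nᵢ, so the curve stays the same or rises. Take ten invented patients with events at months 4, 8, 20 and 40.
- Other six censored at last assessment (6, 12, 18, 24, 24, 24): 9/10 × 7/8 × 4/5 = 0.63 at month 36, then × 0/1 = 0 at month 40. The median is 40 months.
- Same six censored at last visit (24, 36, 48, 60, 72, 96): 9/10 × 8/9 × 7/8 = 0.70 at month 36, then × 4/5 = 0.56 at month 40. The median is not reached.

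This compares one rule with the other. It does not show which is nearer the truth.

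**2. Simple case against the truth, ignoring deaths.** Assume exponential PFS with median 3 years, assessments ending at year 3 and visits continuing. Then S(3) = 0.50 and the true S(5) = exp(−5 ln2/3) = 0.315. If a share q of later progressions is recorded, the last-visit rule gives 0.315 + (1 − q)(0.50 − 0.315):
- q = 0: 0.50
- q = 0.5: 0.41
- q = 1: 0.315, no bias

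The median is 3.0 years under either censoring rule for q = 0.5 and q = 1. At q = 0 both curves stop at the 0.50 boundary. Because section 9.7.2 counts deaths as events, these gaps are upper-end.

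In the same case, with follow-up uniform over 0 to 9 years, moving censoring to the last scan while still counting later progressions gives 5-year PFS of about 0.16 (q = 0.5 or 1), far below 0.315.

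**3. Simulation with deaths (100,000 patients per scenario).** Assumed: 30% never progress; median time to progression in the others 36 months; scans every 3 months until they end; visits every 6 months; median 12 months from progression to death; follow-up uniform over 12 to 120 months.

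| Scans end | Later progressions found at visits | Year-5 PFS, truth | Year-5 PFS, last visit | Median in months, truth | Median in months, last visit |
|---|---|---|---|---|---|
| month 24 | none | 0.518 | 0.595 | 64 | 81 |
| month 24 | half | 0.519 | 0.557 | 65 | 75 |
| month 24 | all | 0.521 | 0.520 | 65 | 66 |
| month 12 | none | 0.519 | 0.605 | 65 | 82 |
| never | not applicable | 0.519 | 0.518 | 65 | 66 |

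The largest excess is 0.605 − 0.519 = 8.6 points. Last-scan censoring with later events still counted gives 0.17 to 0.29 at year 5 when scans end at month 24.

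If the median time to progression in progressors is 12 months instead, with scans to month 24, the median falls while scans continue. Both rules then give 24.0 months (truth 21.6, a gap due to the scan interval), and the year-5 excess of the last-visit rule is 0 to 4 points.

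**4. Chance that the median is not reached.** Sections 9.5 and 9.9 expect fewer than 10 patients a year, and section 9.2.1 divides them by three treatments and two age groups. Group sizes of 5 and 8 are assumptions. With exponential PFS, a true 5-year PFS of 50% to 60% and follow-up uniform over 0 to 9 years, the median is not reached in about 36–48% of runs at n = 5 and 30–46% at n = 8. With follow-up uniform over 1 to 10 years, n = 8 gives 22–38%.

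**The case against.** A reader might infer that PFS will be overstated. The protocol does not support that. It requires visits that outlast tumour assessment and progressions that those visits miss, and the protocol documents neither. The censoring visit is to the treating physician, who may well recognise progression, and section 9.4 has oncologists confirming results for each patient. Nor does any passage show that RECIST is not applied in these charts; section 9.7.2 says that it is. This part stands: the upward error is a possibility of unknown size.

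It also stands that the median, the statistic actually named, does not move when it falls while assessments continue, and that the usual alternative of last-scan censoring can do more harm than the present rule.

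On the median, section 9.7.2 does not say that nothing else will be reported, section 4.9 plans Kaplan-Meier methods for PFS generally, and further PFS summaries could appear in a SAP. A median that is not reached is an ordinary result, not an error. The request for rates is therefore an improvement, not the correction of a mistake.

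PFS is one of several descriptive secondary outcomes in a safety study without hypothesis tests, so the consequence is modest. None of this removes the mismatch that the protocol writes into its own rule.

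**Conclusion.** The concern holds in a limited form. Section 9.7.2 pairs RECIST-based progression with censoring at the last physician visit and does not require that disease status was documented there. PFS can be overstated as a result.

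Under the assumed scenarios the error at year 5 runs from about 0 to +9 points, and the error in the median from about 0 to +17 months. Both are near zero if assessments continue or if visits pick up progression. The median is unaffected if it falls during the period of assessment. These ranges rest wholly on assumed assessment patterns and progression rates, and the protocol offers nothing with which to narrow them.

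The chance of an unreached median, about 22–48% across the cases run, rests on assumed groups of 5 to 8 patients. The change is worth making because it is cheap, but it does not bear on the primary safety objective.

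**What to change.** Amend section 9.7.2 as follows.
- Count progression at the first date on which the treating physician documents it, by imaging or clinically, and record whether RECIST v1.1 was used.
- Censor patients without an event at the last visit or assessment at which disease status was documented. Do not use the last scan alone, because later deaths and progressions would still count as events and PFS would be biased downward.
- State how a death or progression after a long unassessed gap is handled, and define the gap.
- Report the present last-visit rule as a sensitivity analysis.
- Report Kaplan-Meier PFS rates at the OS time points (for example years 1 and 5) beside the median.

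The cost is one more date and one flag to abstract, a few sentences of text, and somewhat earlier censoring in patients seen without a documented disease status. Data collection for the nivolumab and combination groups runs to the end of Q1 2033, so the date can still be collected in the annual abstractions.

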### **9.2.1 Study Population**

The study population will consist of pediatric patients with:

- newly diagnosed or previously treated, advanced (unresectable or metastatic) melanoma who are treated with nivolumab monotherapy, ipilimumab monotherapy, or nivolumab in combination with ipilimumab and enrolled in the DMTR
- melanoma with involvement of lymph nodes or metastatic disease who have undergone complete resection and who are treated with adjuvant nivolumab monotherapy and enrolled in the DMTR

The patients will be divided into 2 cohorts (Cohort 1: 12 to < 18 years old; Cohort 2: < 12 years old), for each treatment (nivolumab monotherapy, ipilimumab monotherapy, or nivolumab in combination with ipilimumab) to make a total of 6 sub-cohorts.

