## **9.7 Data Analysis**

The data provided for pediatric patients will be divided into 2 cohorts, based on age at time of first dose of nivolumab monotherapy, ipilimumab monotherapy, or nivolumab in combination with ipilimumab treatment (index date). Cohort 1 will include patients 12 to under 18 years old at time of enrollment, and Cohort 2 will include patients < 12 years of age at the time of enrollment. Patients that were treated before the nivolumab or ipilimumab marketing approval date will be included and assigned to the appropriate age-based cohort, regardless of timing with respect to date of approval. Interim data on pediatric patients treated with nivolumab monotherapy, ipilimumab monotherapy, or nivolumab in combination with ipilimumab will be reported by BMS to the Pharmacovigilance Risk Assessment Committee in the Periodic Safety Update Report (PSUR), in the interim study report, and in the final study report.

A description of patient and tumor characteristics for all pediatric patients receiving alternative therapies will be provided, for the overall treatment landscape for this patient population.

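### Nivolumab monotherapy OS and PFS mix advanced-disease and completely resected adjuvant patients, so the estimates depend on the chance share of each

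*Protocol*

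**What the plan says.** Section 9.2.1 (repeated in 4.5) defines two populations. The first is "newly diagnosed or previously treated, advanced (unresectable or metastatic) melanoma who are treated with nivolumab monotherapy, ipilimumab monotherapy, or nivolumab in combination with ipilimumab". The second is "melanoma with involvement of lymph nodes or metastatic disease who have undergone complete resection and who are treated with adjuvant nivolumab monotherapy". Nivolumab monotherapy is the only regimen that appears in both.

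The same section divides patients by two age bands and three treatments "to make a total of 6 sub-cohorts". Section 9.7 repeats the age split: "The data provided for pediatric patients will be divided into 2 cohorts, based on age at time of first dose". Table 6-1 lists the same three treatment groups. None of these uses disease setting as a grouping factor.

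In section 9.7.2, OS medians and rates "will be estimated using the Kaplan-Meier methodology for each treatment group", and for PFS: "Median PFS in each treatment group will be derived from the Kaplan Meier estimate". Time to progression is measured to first documented progression, "as assessed by investigator per the Response Evaluation Criteria in Solid Tumors (RECIST) v1.1". PFS uses the same criterion, with death from any cause added. One set of definitions applies to everyone, and no recurrence event is defined for patients who start treatment after complete resection.

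**The concern.** A patient with unresectable or metastatic disease and a patient whose disease has been completely removed start from different points. For the first, the PFS event is growth of existing disease, new disease or death. For the second, it is relapse after surgery or death. A Kaplan-Meier curve over both is a weighted average of two curves, and its median describes neither kind of patient.

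The weights are not designed. Sections 9.5 and 9.9 expect fewer than 10 patients a year over all regimens, ages and settings, so the adjuvant share will be whatever the registry happens to contain. The share may also change between the interim report (Q4 2026) and the final report (Q4 2033), in which case the estimate could move with no change in outcome in either setting.

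A study that is purely descriptive delivers its estimates and little else. It therefore matters that each estimate refers to an identifiable population.

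**Working it through.** **Step 1. Is there room for disease setting in the stated groups?**

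- Age cohorts: 2 (9.2.1, 9.7).
- Treatments: 3 (9.2.1, Table 6-1).
- 2 × 3 = 6, which is exactly the protocol's count. Setting is not a factor.
- Splitting nivolumab monotherapy by setting gives 4 regimen-by-setting groups and 2 × 4 = 8 sub-cohorts.

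The six sub-cohorts of 9.2.1 and the treatment groups of 9.7.2 are different units, but the result is the same on either: adjuvant and advanced nivolumab monotherapy patients fall together.

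**Step 2. Which estimates are affected by explicit text?**

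| Outcome | Estimator in 9.7 | Grouping stated |
|---|---|---|
| OS | Kaplan-Meier | per treatment group |
| PFS | Kaplan-Meier median | per treatment group |
| Time to progression | none; definition only | none |
| Grade 3–4 AEs (9.7.1) | counts, percentages | none |

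The pooling is explicit for OS and PFS only.

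**Step 3. How far could a pooled median move?**

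The protocol gives neither medians nor an adjuvant share, so all inputs here are assumptions. With exponential times, adjuvant share p and medians m_adj and m_adv, the pooled median t solves

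p · 0.5^(t/m_adj) + (1 − p) · 0.5^(t/m_adv) = 0.5.

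Check for m_adv = 9, m_adj = 36, p = 0.50, t = 16.7:

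- 0.5^(16.7/36) = 0.725
- 0.5^(16.7/9) = 0.276
- 0.5 × 0.725 + 0.5 × 0.276 = 0.50, as required.

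| Assumed medians, months (advanced / adjuvant) | p = 25% | p = 50% | p = 75% |
|---|---|---|---|
| 9 / 36 | 11.9 | 16.7 | 25.0 |
| 6 / 36 | 8.3 | 13.0 | 22.9 |
| 6 / 60 | 8.7 | 15.6 | 35.8 |
| 12 / 60 | 16.3 | 24.3 | 39.6 |

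From a 25% to a 75% adjuvant share the pooled median rises by a factor of 25.0/11.9 = 2.1 in the first row and 35.8/8.7 = 4.1 in the third, on case mix alone. These are large-sample values without sampling error.

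**Step 4. Do the protocol's sections agree that adjuvant patients are in?**

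- Sections 9.2.1 and 9.3.2 and the second criterion of 9.2.2 include them.
- The first criterion of 9.2.2 ties the index dose to treatment of advanced melanoma. Read literally, it would leave adjuvant patients out.
- The first secondary objective in 8.2.2 also names advanced disease only.

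These passages conflict and must be reconciled.

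**The case against.** The best case against acting has five parts.

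- **Secondary and descriptive.** The primary endpoint is Grade 3–4 treatment-related AEs (9.1.1). The Annex 2 checklist marks hypotheses, comparators and measures of association as not applicable. This stands, and it lowers the severity. A reader might infer that the mixing will make nivolumab monotherapy look better than the other regimens. The protocol plans no such comparison and gives no case mix, so that claim is not supported.
- **A statistical analysis plan could add a split.** It could. But the protocol itself fixes the groups, the event and the estimator, so the default it sets is the pooled one.
- **Time to progression and AE frequency.** A reader might conclude that these are explicitly pooled too. Section 9.7 states no grouping for either, so that would be an inference from the sub-cohort structure. The firm finding stops at OS and PFS.
- **RECIST.** Nothing shows that a recurrence would go unrecorded as progression. That is correct. What stands is that one progression definition is unclear for patients who begin after complete resection.
- **Small numbers.** Random error in any median may rival the shifts shown, and splitting makes cells smaller. Both are true. Small cells argue for patient listings by setting and do not make a mixed median interpretable.

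**Conclusion.** The concern holds for OS and PFS in the nivolumab monotherapy group. Followed as written, the protocol produces estimates that combine two disease settings and depend on an unplanned adjuvant share. The ipilimumab and combination groups are unaffected, because the adjuvant population is defined for nivolumab monotherapy only.

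The real size of the distortion is unknown. The illustrative shifts rest on assumed exponential curves, medians and shares, and show only that the effect could be material. This is a should-fix for secondary, descriptive outcomes. No test or planned comparison is compromised.

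**What to change.** 1. In 9.7.2, state that nivolumab monotherapy OS and PFS are presented separately for advanced and adjuvant patients, with patient listings where a cell is too small for a curve, and that any pooled figure is not the main result.
2. For adjuvant patients, define the event as first documented recurrence or death (recurrence-free survival) in place of RECIST progression of existing disease.
3. Show the other nivolumab monotherapy summaries (exposure, discontinuation, Grade 3–4 AEs) by setting where counts allow.
4. Reconcile the first inclusion criterion in 9.2.2 and the baseline objective in 8.2.2 with 9.2.1 and 9.3.2.

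**Cost.** This is mainly wording, best settled before the Q4 2026 interim report. Section 9.3.2 already distinguishes adjuvant from advanced exposure, but its itemised variables are dose, frequency, duration and number of infusions. The registry should therefore confirm that setting can be extracted. AJCC stage (9.3.3) may not be enough, because resected metastatic disease also qualifies for the adjuvant population. Recurrence by site is not a listed variable in 9.3.1, so the definition should need only the date of first recurrence, and the registry should confirm that it holds this. The downside is smaller cells: 8 sub-cohorts in place of 6.
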